8.2 Responsibility for Analyses

The statistical analysis of the data obtained from this study will be conducted by, or under the direct auspices of, the Clinical Pharmacology Statistics Department in collaboration with the Quantitative Pharmacology and Pharmacometrics (QP2), and Translational Pharmacology Departments of the Sponsor.

If, after the study has begun, changes are made to the statistical analysis plan stated below, then these deviations to the plan will be listed, along with an explanation as to why they occurred, in the Clinical Study Report.

8.3 Hypotheses/Estimation

Hypothesis (Primary):

- (1) At a dose with sufficient safety, the mean GIR_{max} after single SC administration of MK-1092 in adult subjects with T1DM is between 1.5 and 4.5 mg/kg/min. (Part 3)

8.4 Analysis Endpoints

Primary:

Safety

The primary safety endpoints in this study will include all types of adverse events (AE), in addition to laboratory safety assessments, ECGs, and vital signs.

Pharmacodynamics

The primary pharmacodynamic variable in this study is the glucose infusion rate (GIR) required to maintain blood glucose at each subjects' individual clamp target, following administration of MK-1092 SC or glargine SC. To assess the primary hypothesis in Part 3, the maximal GIR (GIR_{max}) required to maintain the blood glucose target following administration of MK-1092 SC based on LOESS smoothed data during the euglycemic clamp timeframe is of interest.

Secondary:

Pharmacokinetics

MK-1092 SC pharmacokinetic variables of interest include C_{max} , $AUC_{0-\infty}$, CL/F , T_{max} and apparent terminal $t_{1/2}$ of. Similar variables for glargine are also of interest.

Pharmacodynamics

The glucose infusion rate (GIR) required to maintain blood glucose at each subjects' individual clamp target, following administration of MK-1092 SC or glargine SC in Parts 1

and 4 is a secondary endpoint. Specifically, GIR_{max} of MK-1092 SC or glargine SC during the euglycemic clamp timeframe are of interest in Parts 1 and 4.

In addition, time-weighted average based on GIR [TWA(GIR): $AUC(0-t)$ based on GIR values divided by time (t); t= 24, 36 etc.] is also of interest.

Exploratory:

Pharmacodynamics

The glucose infusion rate (GIR) required to maintain blood glucose at each subjects' individual clamp target following administration of MK-1092 SC after the start of Humalog infusion in Part 2 is of interest. The GIR_{max} of MK-1092 after the start of Humalog infusion is of interest in Part 2.

The exploratory pharmacodynamic endpoints in this study also include free fatty acids (FFA; also termed non-esterified fatty acids or NEFA), glycerol and ketones (e.g. β -hydroxybutyrate).

8.5 Analysis Populations

The following populations are defined for the analysis and reporting of data. All subjects will be reported, and their data analyzed, according to the treatment(s) they actually received.

All Subjects as Treated (AST) – All subjects who received at least one dose of the investigational drug. This population will be used for assessments of safety and tolerability.

Per-Protocol (PP) – The set of data generated by the subset of subjects who comply with the protocol sufficiently to ensure that these data will be likely to exhibit the effects of treatment, according to the underlying scientific model. Compliance covers such considerations as exposure to treatment, availability of measurements and absence of major protocol deviations. Major protocol deviators will be identified to the extent possible prior to unblinding by individuals responsible for data collection/compliance, and its analysis and interpretation. Any subjects or data values excluded from analysis will be identified, along with their reason for exclusion, in the CSR. At the end of the study, all subjects who are compliant with the study procedure as aforementioned and have available data from at least one treatment will be included in the primary analysis dataset. This population will be used for the PK and PD analyses.

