A summary of the observed GIR_{max} for the MK-1092 4.0 nmol/kg to 64 nmol/kg dose groups in Part 1 (NHV), for the MK-1092 8.0 nmol/kg and 32 nmol/kg dose group in Part 3 (T1DM), and for the 32 nmol/kg and 16 nmol/kg dose group in Part 4 (T2DM) are provided below. The GIR_{max} for all adult subjects randomized to glargine in any group of Part 1 (Panels A – E), Part 3 (Panel G and H), and Part 4 (Period 1 and 2) are also provided.

| Part 1 GIR_{max} values for MK-1092-001 (4-64 nmol/kg) and Glargine (3.0 nmol/kg), Part 3 GIR_{max} values for MK-1092-001 (8.0 nmol/kg and 32 nmol/kg) and Glargine (3.0 nmol/kg), and Part 4 GIR_{max} values for MK-1092-001 (16 nmol/kg and 32 nmol/kg) and Glargine (3.0 nmol/kg) | | |
|---|---------------------------------|--------------------------------------|
| | Dose | GIR_{max} (mg/kg/min) |
| Part 1 | MK-1092 4.0 nmol/kg | 0.9 |
| | MK-1092 8.0 nmol/kg | 1.7 |
| | MK-1092 16 nmol/kg | 3.1 |
| | MK-1092 32 nmol/kg | 3.3 |
| | MK-1092 64 nmol/kg | 4.4 |
| | Glargine 3.0 nmol/kg (0.5 U/kg) | 2.9 |
| | Part 3 | MK-1092 8.0 nmol/kg |
| MK-1092 32 nmol/kg | | 2.9 |
| Glargine 3.0 nmol/kg (0.5 U/kg) | | 2.5 |
| Part 4 | MK-1092 16 nmol/kg | 1.4 |
| | MK-1092 32 nmol/kg | 1.9 |
| | Glargine 3.0 nmol/kg (0.5 U/kg) | 1.2 |

In Part 1, a dose of 8.0 nmol/kg was safe, well-tolerated, and achieved GIR_{max} of ~1-2 mg/kg/min in healthy adult subjects. Therefore, this dose was tested with Humalog infusion in Part 2 in healthy adult subjects. In Part 2, all healthy subjects achieved GIR_{max} > 4 mg/kg/min. A dose of MK-1092 8.0 nmol/kg was therefore used as the initial dose in Part 3 (adult subjects with T1DM). After 8.0 nmol/kg was tested in Part 2, subsequent panels in Part 1 testing up to 64 nmol/kg have been resumed. A dose of 32 nmol/kg was used as the initial dose in Part 4 (adult subjects with T2DM). A dose of 16 nmol/kg was used as the second dose in Part 4 so as to explore the PD effects of doses below 32 nmol/kg. These doses have been safe and well-tolerated.

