5.2.3 Trial Blinding

Part 2 is open-label; therefore, the Sponsor, investigator and subject will know the treatment administered.

For Parts 1, 3 and 4, a double-blinding technique will be used. MK-1092 and glargine will be prepared and/or dispensed in a blinded fashion by an unblinded pharmacist or qualified trial site personnel. The subject and the investigator who is involved in the treatment or clinical evaluation of the subjects are unaware of the group assignments.

Subjects participating in Parts 1, 3 and 4 will receive injections of MK-1092/glargine and placebo matched to the alternative active treatment (i.e. subjects will receive either MK-1092 and glargine-matched placebo, or glargine and MK-1092-matched placebo).

See Section 7.1.4.2, Subject Blinding/Unblinding, for a description of the method of unblinding a subject during the trial, should such action be warranted.

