7.1.4.2 Subject Blinding/Unblinding

When the investigator or delegate needs to identify the drug used by a subject in case of emergency e.g., the occurrence of serious adverse events, he/she will contact the emergency unblinding call center by telephone and make a request for emergency unblinding. As requested by the investigator or delegate the emergency unblinding call center will provide the information to him/her promptly and report unblinding to the Sponsor. Prior to contacting the emergency unblinding call center to request unblinding of a subject's treatment assignment, the investigator or delegate must enter the intensity/toxicity grade of the adverse events observed, the relation to study drug, the reason thereof, etc., in the medical chart etc. Subjects whose treatment assignment has been unblinded by the investigator/delegate and/or non-study treating physician must be discontinued from study drug, but should continue to be monitored in the trial.

Treatment/Vaccine identification information is to be unmasked ONLY if necessary for the welfare of the subject. Every effort should be made not to unblind the subject unless necessary.

In the event that unblinding has occurred, the circumstances around the unblinding (e.g., date, reason and person performing the unblinding) must be documented promptly, and the Sponsor Clinical Director notified as soon as possible. Only the principal investigator or delegate and the respective subject's code should be unblinded. Other trial site personnel and Sponsor personnel directly associated with the conduct of the trial should not be unblinded.

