8.6 Statistical Methods

Primary

Safety (All Study Parts):

Incidence of adverse experiences will be descriptively summarized. Summary statistics and plots will be generated for the change from baseline values in the vital signs, ECG parameters, and selected laboratory safety parameters for subjects, as deemed clinically

appropriate. Depending on the safety parameter, the difference from baseline will either be computed on the original scale (raw change from baseline) or on the log scale and back-transformed for reporting (percent change from baseline). Summary statistics for the raw laboratory safety tests, ECGs, and/or vital signs may also be computed, as deemed clinically appropriate.

Pharmacodynamics:

GIR (Part 3)

Individual maximal GIR_{max} during the euglycemic clamp timeframe following MK-1092 SC or glargine SC administered to adult subjects with T1DM based on LOESS smoothed data from Part 3 will be analyzed in a fixed effects model with an effect for treatment (i.e. glargine dose, MK-1092 Dose Level 1, MK-1092 Dose Level 2, etc). Means and 95% confidence intervals of GIR_{max} for each treatment/dose will be calculated from the model. To test the Part 3 primary hypothesis, the posterior probability that the true mean GIR_{max} level is within 1.5 and 4.5 mg/kg/min will be calculated for each MK-1092 dose using a non-informative prior. If this posterior probability exceeds 70% for at least one safe and well tolerated dose of MK-1092 SC then the primary research hypothesis for Part 3 will be supported.

Additionally, a non-linear mixed effects model-based analysis may be used to assess the PK/PD (i.e. concentration/GIR) relationship. The model for MK-1092 will be developed using data from Part 3. The model for glargine will be developed using data from Part 3 of the current study and available historical data.

Secondary

Pharmacodynamics:

GIR (Parts 1 & 4):

Individual maximal GIR values (GIR_{max}) during the clamp in Part 1 and Part 4 will be smoothed based on LOESS method.

Model based (similar to Part 3: fixed effect model) statistics such as means, 95% confidence intervals etc. will be provided for each treatment/dose in Part 1.

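### Does restricting the Part 3 GIRmax analysis to the per-protocol set leave the primary result open to exclusions?

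*Combined protocol and SAP*

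**What the plan says.** Section 8.5 defines two populations. All subjects as treated serves safety and tolerability. Of the per-protocol set it says: "This population will be used for the PK and PD analyses". Membership requires sufficient compliance, and the section names three considerations: exposure to treatment, availability of measurements and absence of major deviations. On timing it says: "Major protocol deviators will be identified to the extent possible prior to unblinding by individuals responsible for data collection/compliance". A later sentence begins "At the end of the study, all subjects who are compliant with the study procedure as aforementioned" and places those subjects, if they have data from at least one treatment, in the primary analysis dataset. On reporting: "Any subjects or data values excluded from analysis will be identified, along with their reason for exclusion, in the CSR".

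Section 8.6 fits a fixed-effects model to the Part 3 GIRmax values and computes, for each MK-1092 dose, the posterior probability that the mean lies between 1.5 and 4.5 mg/kg/min. The hypothesis is supported on this condition: "If this posterior probability exceeds 70% for at least one safe and well tolerated dose of MK-1092 SC". No second population is named for this analysis. Section 8.7 states that the hypotheses are not assessed by formal testing with type I error control.

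**The concern.** Three features together look uncomfortable. The primary pharmacodynamic result comes from one population only. Membership of that population is partly a judgement, with no itemised list of excluding deviations. And the dataset appears to be settled late, when group results are already known: section 4.1.2 prints GIRmax by treatment, and its introduction says that the glargine values for "Part 3 (Panel G and H), and Part 4 (Period 1 and 2) are also provided".

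Each dose has six subjects. If someone who knew the results could decide whose clamp counted, a dose near 1.5 or 4.5 might be moved across the 70% threshold. The study report would show who was left out and why, but not the result with that subject included. At stake would be the credibility of the per-dose posteriors, means and intervals, and possibly of the primary conclusion.

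**Working it through.** **Inputs.** SD 0.44, six subjects per dose and a 70% threshold (section 8.8, Table 11); window 1.5 to 4.5 and a non-informative prior (section 8.6); preliminary Part 3 mean of 2.9 at 32 nmol/kg (section 4.1.2). The documents give no exclusion rate, so exclusion patterns below are assumptions.

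**Method.** With sample mean m, sample SD s and n subjects, the posterior probability is F((4.5 − m)/(s/√n)) − F((1.5 − m)/(s/√n)), where F is the t distribution function with n − 1 df. Support means a value above 0.70. Each case used 200,000 simulated panels.

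**Reproducing Table 11.** For true means 1, 1.5, 2, 4, 4.5 and 5 the plan states 0.03%, 30.9%, 98.7%, 98.6%, 29.40% and 0.06%. The recalculation gives 0.05%, 30.1%, 98.6%, 98.6%, 29.9% and 0.05%. It gives 100% from 2.5 to 3.5, as the plan does.

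**Effect of excluding one of six on support for a dose.** Most unfavourable means the lowest value for means below 3 and the highest for means above 3.

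| True mean | All six | One dropped at random | Most unfavourable always dropped | Panels whose result changes with a random drop |
|---|---|---|---|---|
| 1.5 | 30.0% | 30.1% | 55.4% | 11.9% |
| 2.0 | 98.7% | 97.5% | 99.8% | 1.8% |
| 2.9 | 100% | 100% | 100% | 0% |
| 4.5 | 29.9% | 29.9% | 55.2% | 11.7% |

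The rise to 55% is a bound. It needs a true mean on a limit and selection against the worst value in every panel. If that happened in 10% of panels, support at 1.5 would be 0.9 × 30.0 + 0.1 × 55.4 = 32.5%; in 25%, 0.75 × 30.0 + 0.25 × 55.4 = 36.4%. The 12% in the last column is the ordinary difference between five and six observations at a limit; the long-run rate does not move.

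**Effect on the mean.** The lowest of six normal values lies on average 1.267 SD below the mean, so always dropping it shifts the mean by 1.267 × 0.44 / 5 = 0.11 mg/kg/min. The 95% half-width with six subjects is t(0.975, 5 df) × 0.44/√6 = 2.571 × 0.180 = 0.46. Even the bounding shift is about a quarter of that.

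**At the tabulated mean of 2.9.** With s = 0.44 the posterior is above 0.99 for n = 6, 5 or 4. With twice that SD (0.88, assumed) it is 0.99, 0.98 and 0.96. With six subjects, s would have to be about 3.2, some seven times the planning value, for the posterior to fall to 70%.

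**When exclusions are decided.** The sentence opening with "At the end of the study, all subjects who are compliant with the study procedure as aforementioned" refers back to the compliance process just described, which takes place before unblinding as far as possible. It reads naturally as saying when the dataset is assembled, not as moving the decisions to the end of the study.

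**Who knows what.** Section 4.1.2, which holds the GIRmax table, also states that allocation in Parts 1, 3 and 4 is still blinded. Section 5.2.3 makes the exception explicit for Part 2 only: "Part 2 is open-label; therefore, the Sponsor, investigator and subject will know the treatment administered". Section 7.1.4.2, on emergency unblinding, adds: "Other trial site personnel and Sponsor personnel directly associated with the conduct of the trial should not be unblinded". Group means do not reveal an individual's allocation, and nothing shows that those judging compliance saw by-treatment results.

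**Room for judgement.** Part 3 dosing is one injection, witnessed by trial staff (section 7.1.1.8), in subjects resident in the unit (section 7.1.4.3). A subject without usable clamp data has no GIRmax and could not enter an all-treated run either, so the two sets may well coincide.

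**The case for a change.** The strongest counter-argument is that blinding protects less here than in a comparative trial. Each dose is judged against a fixed window, not against glargine, and infusion rates are recorded at the bedside (section 7.1.3.2.4), so hiding allocation does not hide the outcome. Section 8.5 also allows data values, not only subjects, to be excluded. Doses near a limit are plausible: section 4.1.2 gives Part 1 means of 1.7 at 8.0 nmol/kg, the Panel G dose, and 4.4 at 64 nmol/kg, the ceiling for Panel J. At a true mean of 1.7, support is 72% with all six, 89% if the least favourable value is always dropped and about 50% if the most favourable is; at 4.4 the figures are 51%, 75% and about 30%.

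The facts and the arithmetic stand, and an all-treated run would cost little. But the figures again assume that selection by outcome occurs every time, and no document suggests that it occurs at all. Nor does anything prespecified depend on whether one particular dose passes: the rule asks for at least one, and section 2.1 has Panel J decided on all available data from Panels G and H. The high rate of glucose sensor failure in the summary of changes concerns Part 4, with back-up measurement on a second analyser; none is reported for Part 3.

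**Conclusion.** The concern does not hold. Using a per-protocol set for pharmacodynamics in this Phase 1 clamp study, with deviators identified before unblinding as far as possible and every exclusion reported with its reason, is not shown to give a wrong or worse result. One exclusion changes nothing for a dose at 2.9 (100% support in every case at SD 0.44), and one dose is enough. The largest computed effect, 30% to 55%, belongs to an assumed bound at a limit of the window; exclusion unrelated to the outcome leaves 30% at 30%. An all-treated run would be an optional extra that leaves the main analysis unchanged and matches it exactly if nobody with a GIRmax value is excluded.

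This rests on the planning SD of 0.44, taken from another compound in healthy adults, and on a preliminary 2.9 reported without an SD; the margin up to about 3.2 makes the first assumption uncritical. It also rests on 32 nmol/kg continuing to be judged safe and well tolerated, as section 4.1.2 reports. The Part 3 value at 8.0 nmol/kg cannot be read in the text available, but the primary conclusion does not depend on it.

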8.6 Statistical Methods

Primary

Safety (All Study Parts):

Incidence of adverse experiences will be descriptively summarized. Summary statistics and plots will be generated for the change from baseline values in the vital signs, ECG parameters, and selected laboratory safety parameters for subjects, as deemed clinically

appropriate. Depending on the safety parameter, the difference from baseline will either be computed on the original scale (raw change from baseline) or on the log scale and back-transformed for reporting (percent change from baseline). Summary statistics for the raw laboratory safety tests, ECGs, and/or vital signs may also be computed, as deemed clinically appropriate.

Pharmacodynamics:

GIR (Part 3)

Individual maximal GIR_{max} during the euglycemic clamp timeframe following MK-1092 SC or glargine SC administered to adult subjects with T1DM based on LOESS smoothed data from Part 3 will be analyzed in a fixed effects model with an effect for treatment (i.e. glargine dose, MK-1092 Dose Level 1, MK-1092 Dose Level 2, etc). Means and 95% confidence intervals of GIR_{max} for each treatment/dose will be calculated from the model. To test the Part 3 primary hypothesis, the posterior probability that the true mean GIR_{max} level is within 1.5 and 4.5 mg/kg/min will be calculated for each MK-1092 dose using a non-informative prior. If this posterior probability exceeds 70% for at least one safe and well tolerated dose of MK-1092 SC then the primary research hypothesis for Part 3 will be supported.

Additionally, a non-linear mixed effects model-based analysis may be used to assess the PK/PD (i.e. concentration/GIR) relationship. The model for MK-1092 will be developed using data from Part 3. The model for glargine will be developed using data from Part 3 of the current study and available historical data.

Secondary

Pharmacodynamics:

GIR (Parts 1 & 4):

Individual maximal GIR values (GIR_{max}) during the clamp in Part 1 and Part 4 will be smoothed based on LOESS method.

Model based (similar to Part 3: fixed effect model) statistics such as means, 95% confidence intervals etc. will be provided for each treatment/dose in Part 1.

For Part 4, a linear mixed effects model containing a fixed effect for treatment (MK-1092, Glargine), a nested effect from subjects within treatment (subjects within treatment), an interaction between treatment and period (treatment by period: Period = Period 1, 2, 3) and a random effect due to subjects will be used. Kenward and Roger's method will be used to calculate the denominator degrees of freedom for the fixed effects. Model based statistics such as means, 95% confidence intervals etc. will be provided for each treatment/dose.

TWA(GIR) (Part 1, 3 and 4):

Time-weighted average based on GIR [TWA(GIR): $AUC(0-t)$ based on GIR values divided by time (t)] is also of interest. Model based (similar to GIR_{max} in Part 3) statistics such as

means, 95% confidence intervals etc. will be provided for each treatment/dose. AUC will be computed based on all observed GIR values.

Pharmacokinetics (All Study Parts):

Geometric means and 95% confidence intervals (non-model based) will be provided for C_{max}, AUC_{0-∞} and CL/F if calculated for the given study part, following SC administration by treatment.

Individual values will be listed for each PK parameter by treatment and the additional following (non-model-based) descriptive statistics will be provided: N (number of subjects with non-missing data), arithmetic mean, standard deviation, arithmetic percent CV (calculated as 100 x standard deviation/arithmetic mean), median, minimum, maximum, geometric mean, and geometric percent CV (calculated as 100 x sqrt(exp(s²) - 1), where s² is the observed variance on the natural log-scale). For T_{max}, median, minimum and maximum will be provided.

Exploratory

Pharmacodynamics

GIR (Part 2):

Individual values for GIR_{max} based on LOESS smoothed data after the start of Humalog administration in Part 2 will be listed only. Descriptive statistics will be provided also.

Free Fatty Acids (FFA):

Individual change from baseline serum FFA values in all Parts except Part 2, where baseline is the predose value, following SC administration of MK-1092 or glargine will be summarized with descriptive statistics and plotted over time. Formal treatment comparisons (MK-1092 versus glargine) may also be performed if deemed necessary. FFA values for each subject in Part 2 will be listed only.

Glycerol:

Individual change from baseline glycerol values, where baseline is the predose value, will be analyzed in a similar fashion as FFA.

Ketones (β-hydroxybutyrate):

Individual change from baseline β-hydroxybutyrate values, where baseline is the predose value, will be analyzed in a similar fashion as FFA.

Pharmacokinetics (Part 2):

General PK profile for Humalog IV may be explored descriptively.

General:

For all analyses, data will be examined for departures from the assumptions of the statistical model(s) as appropriate; e.g., heteroscedasticity, nonnormality of the error terms. Distribution-free methods may be used if a serious departure from the assumptions of the models(s) is observed, or suitable data transformations may be applied.

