In Part 4, subjects will be blinded in a double-dummy fashion, so that each subject will receive MK-1092/glargine and a matched placebo to the alternative active treatment. Dosing in the first period of this part will use a SC dose no higher than one that has been determined to be safe and tolerated in Part 1. At the time of protocol amendment 03, doses ≤ 64 nmol/kg have fulfilled these criteria. At the time of protocol amendment 04, a dose of 32 nmol/kg was administered in Period 1 and a dose of 16 nmol/kg was administered in Period 2. Dosing in Period 3 of Part 4 will commence upon review of the safety data from previous periods within Part 4 and determination of an acceptable safety profile to continue dose escalation. Up to 3 doses of MK-1092 will be administered in successive periods. The glargine dose will be the same in all periods of Part 4 and is expected to achieve $GIR_{max} \sim 2$ mg/kg/min. The MK-1092 doses will include, and may escalate beyond, the expected therapeutic insulin concentration range for a GIR_{max} of $\sim 1-2$ mg/kg/min. Doses in Part 4 will not exceed 64 nmol/kg SC, which is the highest planned dose in the clinical program. Unlike in Parts 1-3, in Part 4 the same subjects will participate in each period (N=6 receiving MK-1092, N=3 receiving glargine). Subjects in Part 4 who are randomized to MK-1092 in Period 1 will receive MK-1092 in the subsequent periods, and subjects in Part 4 who are randomized to glargine in Period 1 will receive glargine in the subsequent periods. All subjects will complete dosing in Period 1 prior to the start of Period 2, and all subjects will complete dosing in Period 2 prior to the start of Period 3. In addition, determination of an acceptable safety profile in Period 1 will be required prior to starting Period 2 and an acceptable safety profile in Period 2 will be required prior to starting Period 3. At least 7 days will occur between dose administrations in Part 4 to allow for washout. Furthermore, an operational pause will be implemented between Period 2 and Period 3 in Part 4 only to allow sufficient time for analysis of data collected in prior periods of Part 4 and/or panels of Parts 1 and 3 to

inform on dose decisions related to Period 3. The objectives for this part will assess safety and tolerability of the SC injection, PK, and PD endpoints for MK-1092 and glargine in adult subjects with T2DM.

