8.0 STATISTICAL ANALYSIS PLAN

8.1 Statistical Analysis Plan Summary

This section contains a brief summary of the statistical analyses for this trial. Full details can be found beginning in Section 8.2.

Statistical Methods

Safety (All Study Parts):

Incidence of adverse experiences will be descriptively summarized. Summary statistics and plots will be generated for the change from baseline values in the vital signs, ECG parameters, and selected laboratory safety parameters for subjects, as deemed clinically appropriate. Depending on the safety parameter, the difference from baseline will either be computed on the original scale (raw change from baseline) or on the log scale and back-transformed for reporting (percent change from baseline). Summary statistics for the raw laboratory safety tests, ECGs, and/or vital signs may also be computed, as deemed clinically appropriate.

Pharmacodynamics:

Individual maximal GIR values (GIR_{max}) during the clamp of MK-1092 SC or glargine SC administered to adult subjects with T1DM based on LOESS smoothed data from Part 3 will be analyzed in a fixed effects model with treatment as fixed effect (i.e. glargine, MK-1092 Dose Level 1, MK-1092 Dose Level 2, etc.). Means and 95% confidence intervals of GIR_{max} for each treatment/dose will be calculated from the model. Similar analysis (based on a slightly different model) will be done using data from Part 4 (T2DM). To test the Part 3 primary hypothesis, the posterior probability that the true mean GIR_{max} level is within 1.5 and 4.5 mg/kg/min will be calculated for each MK-1092 dose using a non-informative prior. If this posterior probability exceeds 70% for at least one safe and well tolerated dose of MK-1092 SC then the primary research hypothesis for Part 3 will be supported. There is no formal hypothesis testing (based on GIR) associated with Part 4. Posterior probabilities may be provided, if necessary.

Individual maximal GIR values (GIR_{max}) during the clamp in Part 1 will be determined based on LOESS smoothed data. Model based (similar to Part 3) statistics such as means, 95% confidence intervals etc. will be provided for each treatment/dose.

Pharmacokinetics (All Study Parts):

Geometric means and 95% confidence intervals will be provided for C_{max}, AUC_{0-∞} and CL/F, if calculated for the given study part, following SC administration by treatment.

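### The TWA(GIR) paragraph in Section 8.6 sends Part 4 to the Part 3 treatment-only model; read literally, the pooled glargine confidence interval is too narrow when repeated values within a subject are positively correlated

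*Combined protocol and SAP*

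**What the plan says.** Section 8.6 handles TWA(GIR) in one paragraph, headed "TWA(GIR) (Part 1, 3 and 4". It promises "Model based (similar to GIR_{max} in Part 3) statistics such as" means and 95% confidence intervals for each treatment/dose, and names no other model.

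The model it refers to is in the Part 3 GIR text of the same section. There, GIRmax "will be analyzed in a fixed effects model with an effect for treatment (i.e. glargine dose, MK-1092 Dose Level 1, MK-1092 Dose Level 2, etc"; no subject or period term is listed.

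Part 4 GIRmax has its own model, under the heading for GIR in Parts 1 and 4: "For Part 4, a linear mixed effects model containing a fixed effect for treatment (MK-1092, Glargine"). It also has a treatment-by-period interaction, a random subject effect, and Kenward-Roger degrees of freedom, and it separately lists "a nested effect from subjects within treatment (subjects within treatment"). That heading's text concerns GIRmax. Nothing in the plan says that this model also serves TWA(GIR).

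The reason for a separate Part 4 model is the design in Section 2.1. Part 3 uses different subjects in each panel, but "in Part 4 the same subjects will participate in each period": six on MK-1092 and three on glargine, with the glargine dose unchanged throughout.

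**The concern.** A treatment-only model assumes that every record is independent. With one glargine level, Part 4 would put all glargine periods into one cell: up to 3 × 3 = 9 values from only three people. If a subject's TWA(GIR) values are positively correlated across periods, the standard error is too small and the interval too narrow.

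The plan already recognises the repeated measures for Part 4 GIRmax. TWA(GIR) comes from the same clamps in the same subjects, and no reason is given for a different model.

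At stake is the Part 4 glargine reference interval for a secondary endpoint. Glargine is the pharmacodynamic comparator (Section 4.2.2.1), so readers will set the MK-1092 dose means against it.

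**Working it through.** **The plan's own figure.** No precision or power is stated for Part 4 TWA(GIR). The only stated power figure is Table 10/11, for Part 3 GIRmax. Simulating n = 6, SD 0.44, a flat prior and a 70% threshold, with the SD estimated per dose, gives 30.1% at a true mean of 1.5 (stated 30.9%) and 98.7% at 2 (stated 98.7%). The table reproduces, and this point does not affect it.

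**Inputs.**
- 6 MK-1092 and 3 glargine subjects, the same in each period (Section 2.1).
- Up to three periods (Section 2.2), so two is also examined.
- One glargine level (Section 8.6, Part 3 model).
- 95% intervals (Section 8.6).
- Within-subject correlation ρ: not in the documents, so assumed from 0 to 0.8.
- Also assumed: normal data, compound symmetry, total variance σ², all nine subjects completing every period, a different MK-1092 dose each period, and no period effect.

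**Literal model, three periods.** 9 × 3 = 27 records and 4 levels leave 27 − 4 = 23 residual df.
- Standard error used by the model for the glargine mean: s/√9.
- True standard error: σ√((1 + 2ρ)/9).
- True over independence standard error: √(1 + 2ρ). For ρ = 0.5 this is √2 = 1.41.
- The residual variance is also slightly low: E[s²] = σ²(23 − 2ρ)/23. For ρ = 0.5 this is 22/23 = 0.957σ².

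**Two periods.** 18 records and 3 levels leave 15 df. The standard error ratio is √(1 + ρ).

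**Actual coverage of the nominal 95% interval under the literal model** (200,000 simulations per setting):

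| ρ | √(1 + 2ρ) | Glargine pooled, 3 periods | Glargine pooled, 2 periods | MK-1092 dose mean, 3 periods | MK-1092 dose mean, 2 periods |
|---|---|---|---|---|---|
| 0 | 1.00 | 95.0% | 95.1% | 95.0% | 95.0% |
| 0.1 | 1.10 | 92.7% | 93.9% | 94.9% | 94.8% |
| 0.3 | 1.26 | 87.7% | 91.5% | 94.5% | 94.6% |
| 0.5 | 1.41 | 82.9% | 88.7% | 93.9% | 94.3% |
| 0.7 | 1.55 | 77.8% | 85.9% | 93.1% | 93.7% |
| 0.8 | 1.61 | 75.6% | 84.3% | 92.6% | 93.2% |

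A separate run of 100,000 simulations gave 87.8, 82.7, 77.7 and 75.7% for pooled glargine with three periods at ρ = 0.3, 0.5, 0.7 and 0.8.

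**If glargine is kept separate by period** (six cells, 27 − 6 = 21 df), the independence model covers 94.8, 94.5, 93.8 and 93.5% at ρ = 0.3, 0.5, 0.7 and 0.8. The loss comes from pooling the same subjects' periods.

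**Mixed model** (balanced-data equivalent, subject within treatment random and entered once). The glargine mean over periods uses the between-subject mean square on (6 − 1) + (3 − 1) = 7 df and covers 95.0 to 95.1%. MK-1092 dose means with Satterthwaite df cover 94.8 to 95.2%.

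**The case against.** The best reply is that the literal reading is not what the authors meant. The rule asks for a similar model, not the same one. Section 8.1, straight after describing the Part 3 model, says "Similar analysis (based on a slightly different model) will be done using data from Part 4 (T2DM"), so similarity to Part 3 can include the mixed model. Where the plan means the fixed effects model itself, for Part 1, it says so: "Model based (similar to Part 3: fixed effect model) statistics such as means". The TWA(GIR) sentence lacks that qualifier and follows directly after the Part 4 mixed model. This stands in part: the wording is open, and the text does not prove that a wrong analysis will be run. But the Section 8.1 remark is attached to GIRmax, Section 8.1 does not mention TWA(GIR), and the sentence names Part 3 when the Part 4 model was there to cite.

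Second, the size depends on pooling and on an assumed correlation. Both are true. Pooling is nevertheless the natural reading: the cited model has one glargine level, and the interim table in Section 4.1.2 reports a single Part 4 glargine GIRmax (1.2) for Periods 1 and 2 together. The direction of the error holds for any positive correlation.

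Third, little depends on it. Secondary objective 3 concerns MK-1092, Part 4 has no formal GIR hypothesis, and no p-value testing is used. This stands and sets the weight of the point.

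Fourth, Section 5.9 lets a Part 4 replacement subject start at the next dose level. That would reduce repeated records per subject and soften the loss.

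The general assumption check in Section 8.6 does not close the gap. Its examples are unequal variance and non-normality, and its remedies, distribution-free methods or transformations, do not deal with dependence between periods.

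**Conclusion.** The concern holds as a minor one. As written, the TWA(GIR) rule points Part 4 to a model that ignores repeated measurement, and no other text overrides it. On the literal reading, with glargine pooled and correlations of 0.3 to 0.8, coverage of the 95% glargine interval falls to about 88 to 76% with three periods and 91 to 84% with two. At zero correlation there is no loss.

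The correlation range is an assumption, as are compound symmetry and complete data. MK-1092 dose means, each from six different subjects, keep 93 to 95% coverage. The endpoint is secondary and for estimation only. The primary Part 3 hypothesis and Tables 10 and 11 are unaffected.

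**What to change.** Limit the reference to the Part 3 model to Parts 1 and 3. State that Part 4 TWA(GIR) uses the Part 4 GIRmax linear mixed model: treatment, treatment-by-period, subject within treatment as the random effect, and Kenward-Roger degrees of freedom. Enter the subject term once, since the current text lists both a nested and a random subject effect. State that MK-1092 is reported by dose/period and that the glargine mean is the equal-weight average over the periods conducted.

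The drafting cost is one or two sentences, and the GIRmax code can be reused. The statistical cost is a wider glargine interval, reflecting that only three subjects inform it. At ρ = 0.3, 0.5, 0.7 and 0.8 it is 1.43, 1.62, 1.80 and 1.89 times as wide with three periods, and 1.26, 1.36, 1.47 and 1.52 times with two. Even at zero correlation it is 1.11 times as wide with three periods, because 7 df replace 23. Over ρ = 0.3 to 0.8, MK-1092 dose-mean intervals become 1.04 to 1.13 times as wide with three periods and 1.03 to 1.10 times with two.
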